4.3.2 Dose Modifications and Management of Toxicity

Dose modifications are permitted in Cycle 1 only in the event of a DLT.

Dose modifications of epacadostat will be made per the dose escalation table.

1. If dose reduction of epacadostat is necessary:

- The dose should be reduced stepwise based on the dose escalation table. The patient should be monitored for approximately 10 to 14 days at each dose level.

Treatment or visit delays for public holidays or weather conditions do not constitute a protocol violation. After cycle 2, patients who have benefit are allowed to request treatment interruptions for personal reasons up to three weeks. Longer treatment interruptions must be approved by the PI and the drug sponsor.

The following dose modification rules will be used with respect to potential toxicity. Toxicity will be assessed according to the NCI Common Terminology Criteria for Adverse Events Version 4.03 (CTCAE v4.03).

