	Diarrhea with hyperactive bowel sounds	Ocular clonus (slow continuous lateral eye movements)	Agitation and hypervigilance	Renal Failure
	Diaphoresis with normal skin color	Myoclonus		Disseminated intravascular coagulopathy (secondary to hyperthermia)
4.3.11 Severe	Temperature often more than 41 0C (Secondary to increased tone)	Increased muscle tone (lower limb > upper)	Delirium	As above
		Spontaneous clonus	Coma	
		Substantial myoclonus or hyperreflexia		

¹ Boyer EW, Shannon M. The serotonin syndrome. New Engl J Med 2005;352: 1112-1120.

Dose Modification versus Dose Interruption

Epacadostat, pembrolizumab and tavo-EP may be held for up to 6 weeks as clinically indicated or required due to treatment associated AEs but dose reductions are not permitted.

Dosing interruptions of all agents may be permitted in the case of medical/surgical events or logistical reasons not related to study therapy (eg, elective surgery, unrelated medical events, subject vacation, and/or holidays). Subjects should be placed back on study therapy within 6 weeks of the scheduled interruption. The reason for interruption should be documented in the subject's study record.

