5.2 Safety Stopping Rules

Clinical evaluations including laboratory and clinical safety assessments will be performed at 3-week intervals for patients who are actively receiving treatment on study. For patients in the follow-up portions of the study who are not actively receiving therapy, evaluations will be performed at 12-week intervals. Safety will be assessed during the study by documentation of adverse events (AEs), clinical laboratory tests, physical examination, vital sign measurements, and Eastern Cooperative Oncology Group (ECOG) performance status.

Lead-In Period and De-Escalation

1. If, at any time, 2 or more of the first 6 safety-evaluable patients experience grade 3 or higher treatment-associated adverse events within the first 30 days of initiation of treatment, then no further patients will be enrolled at the current dose level.
2. After 6 patients have been enrolled on study, enrollment will be halted for 30 days for completion of lead-in safety analysis. If 0-1 patients experience grade 3 or higher treatment-associated adverse events within the first 30 days of initiation of treatment, then additional patients may be enrolled at the current dose level.
3. If enrollment is halted at any time during the lead-in period due to treatment-associated adverse events, the UCSF DSMB will review all available safety data with the Principal Investigator. Based on this review, study discontinuation or reduction of the epacadostat dose may be recommended. No further patients will be enrolled on study without the approval of the DSMB. If the DSMB allows additional patients to enroll, the lead-in period will be repeated at the new dose level with a maximum of 6 additional patients enrolled prior to follow-up safety analysis. At the discretion of the DSMB, patients who are currently on study may continue treatment at the reduced dose level.
4. Patients who discontinue treatment on study within 30 days of initiation of therapy for reasons other than treatment-associated toxicity will be deemed inevaluable for safety and replaced for safety analysis.

Mid-Study Interim Safety Analysis

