11.1.1.1 Definitions

Evaluable for toxicity

All patients will be evaluable for toxicity from the time of their first treatment with epacadostat, pembrolizumab, or tavo-EP.

Evaluable for objective response

Only those patients who have measurable disease present at baseline, have received at least one cycle of therapy, and have had their disease re-evaluated will be considered evaluable for response. These patients will have their response classified according to the definitions stated below. (Note: Patients who exhibit objective disease progression prior to the end of Cycle 1 will also be considered evaluable).

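### Lead-in evaluability has no minimum-exposure condition, so an event-free patient who missed most Cycle 1 dosing for a non-toxicity reason stays in the escalation denominator by default

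*Combined protocol and SAP*

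**What the plan says.** **Evaluability.** Section 5.2, lead-in item 4, gives one ground for inevaluability: "Patients who discontinue treatment on study within 30 days of initiation of therapy for reasons other than treatment-associated toxicity will be deemed inevaluable". Such patients are replaced. The synopsis repeats this. Section 11.1.1.1 adds: "All patients will be evaluable for toxicity from the time of their first treatment with epacadostat, pembrolizumab, or tavo-EP". No section sets a minimum amount of epacadostat, pembrolizumab or tavo-EP for a patient to count in the escalation decision.

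**Interruption.** The subsection on dose modification versus dose interruption, at the end of Section 4.3.3, states: "Dosing interruptions of all agents may be permitted in the case of medical/surgical events or logistical reasons not related to study therapy". Its examples are "elective surgery, unrelated medical events, subject vacation, and/or holidays", and its limit is "Subjects should be placed back on study therapy within 6 weeks of the scheduled interruption". It also says that the three agents "may be held for up to 6 weeks as clinically indicated or required due to treatment associated AEs". It makes no exception for Cycle 1 or the lead-in.

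Section 4.3.2 says: "After cycle 2, patients who have benefit are allowed to request treatment interruptions for personal reasons up to three weeks". Longer interruptions need approval from the PI and the drug sponsor. The same section limits Cycle 1 dose modifications to the event of a DLT, without saying whether an interruption is a modification.

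**Window.** A DLT must occur in Cycle 1 (Section 4.3.1). Cycle 1 lasts 42 days in Table 3-1, Table 4-1 refers to 28-day cycles, and the synopsis and Section 5.2 use 30 days.

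**The concern.** An escalation rule needs each counted patient to have had a fair chance of showing toxicity at the dose under test. Someone who starts, pauses for an unrelated operation and later resumes has not discontinued, so item 4 does not replace them. If they have no event, they add to the denominator without having tested the dose.

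The resulting error runs one way, towards passing the level. The decision at stake is the move from 300 mg to 600 mg BID, and the lead-in result sets the epacadostat dose for Arm A (synopsis, Table 4-2).

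**Working it through.** The plan gives no operating characteristics for its escalation rules, so there is no figure to reproduce. There are two checks.

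**1. Can a permitted pause cover the observation window?** Six weeks is 42 days.

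- 28-day cycle (Table 4-1): 42/28 = 150%
- 30 days (synopsis, Section 5.2): 42/30 = 140%
- 42-day Cycle 1 (Table 3-1): 42/42 = 100%

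On the Table 3-1 calendar, a pause starting after Day 1 could miss tavo-EP on Days 5 and 8, pembrolizumab on Day 22 and most epacadostat doses. The three-week allowance in Section 4.3.2 applies only after cycle 2, so it lies outside the window.

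**2. How much does one such patient change the chance of passing?** The two rules count different events:

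- Table 4-3 counts DLTs. A level passes with 0 of 3, or with 1 of 3 followed by 0 of 3.
- The 0-1 of 6 rule (synopsis and Section 5.2, item 2) counts grade 3 or higher treatment-associated AEs within 30 days. The synopsis then opens the next dose level; Section 5.2 allows further patients at the current one.

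Let p be the true event rate in an exposed patient, q = 1 − p, and s the risk in the one barely exposed patient (among the first three for Table 4-3). The documents give no event rate, so p is assumed and varied.

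- Table 4-3, all exposed: q³ + 3pq²·q³
- Table 4-3, one barely exposed: (1 − s)q² + [s·q² + 2(1 − s)pq]·q³
- 0-1 of 6, all exposed: q⁶ + 6pq⁵
- 0-1 of 6, one barely exposed: (1 − s)(q⁵ + 5pq⁴) + s·q⁵

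At p = 0.33, q = 0.67:

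- Table 4-3, all exposed: 0.3008 + 0.4444 × 0.3008 = 0.434
- Table 4-3, s = 0: 0.4489 + 0.4422 × 0.3008 = 0.582
- Table 4-3, s = 0.165: 0.3748 + 0.4433 × 0.3008 = 0.508
- 0-1 of 6, all exposed: 0.0905 + 0.2673 = 0.358
- 0-1 of 6, s = 0: 0.1350 + 0.3325 = 0.468
- 0-1 of 6, s = 0.165: 0.835 × 0.4675 + 0.165 × 0.1350 = 0.413

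The same formulas over a range of assumed rates:

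| p | Table 4-3: all exposed | one at half risk | one at no risk | 0-1 of 6: all exposed | one at half risk | one at no risk |
|---|---|---|---|---|---|---|
| 0.20 | 0.709 | 0.756 | 0.804 | 0.655 | 0.696 | 0.737 |
| 0.33 | 0.434 | 0.508 | 0.582 | 0.358 | 0.413 | 0.468 |
| 0.40 | 0.309 | 0.386 | 0.464 | 0.233 | 0.285 | 0.337 |
| 0.50 | 0.172 | 0.242 | 0.312 | 0.109 | 0.148 | 0.188 |

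One barely exposed patient adds roughly 8 to 16 percentage points if that patient carries no risk, and roughly 4 to 8 points if half the risk remains.

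**The case against.** A reader might infer that the plan plainly allows a six-week vacation in Cycle 1 and declares the patient DLT-free. The documents do not support that. Section 4.3.2 places personal-reason breaks after cycle 2, for patients with benefit and up to three weeks, so a Cycle 1 vacation is contradicted rather than clearly permitted. The later subsection says only that interruptions may be permitted. No section states that an interrupted patient is DLT-free; the patient simply has no stated route out of the denominator. The contradiction does not close the gap, because unrelated medical events, elective surgery and logistics are not obviously personal reasons.

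Other text also helps the plan:

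- The Cycle 1 limit on dose modifications might be meant to cover interruptions, but the later subsection's title treats the two as different things.
- The synopsis describes 30 days of triplet therapy before escalation, but does not make receiving it a condition of evaluability.
- Section 4.3.3 requires interruptions longer than two weeks to be discussed with the principal investigator before treatment resumes.
- Section 5.2 has weekly lead-in safety calls. Appendix 2 has DSMC review of each cohort's data and Chair or Vice Chair approval of escalation.

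These safeguards are real, and a patient off drug for weeks would probably be noticed. None says how to count that patient. The contents Appendix 2 lists for the escalation report are cohort dose, adverse events and DLTs, not dosing received.

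The probabilities are also open to challenge. The event rates are assumed, zero risk is an upper bound because every counted patient has started treatment, and the documents do not indicate how often such interruptions would occur. All three points stand, which is why the half-risk figures are shown.

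**Conclusion.** The concern holds as a gap in the evaluability rule. Discontinuation is the only ground for replacement, toxicity evaluability starts at first treatment, and a pause as long as any of the three stated windows is possible without discontinuing. An event-free patient with little Cycle 1 exposure for a non-toxicity reason is therefore kept by default, and the bias is towards escalation.

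If one such patient is among the first three, at an assumed true event rate of 33%, the chance of passing under Table 4-3 rises from 0.43 to between 0.51 (half risk) and 0.58 (no risk). Under the 0-1 of 6 rule it rises from 0.36 to between 0.41 and 0.47. These figures are conditional on such a patient occurring. They do not show that the escalation decision will in fact rest on unexposed patients, and DSMC review makes that less likely.

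**What to change.** 1. **Item 4, in Section 5.2 and the synopsis.** Add a second ground for inevaluability, replaced under the existing rule, that requires all of the following: no DLT; no grade 3 or higher treatment-associated AE; and more than a pre-stated share of planned dosing in the DLT window missed for reasons other than treatment-associated toxicity. The share should be fixed before the lead-in data are reviewed.
2. **Patients who always count.** State that anyone with a DLT, a grade 3 or higher treatment-associated AE, or doses held for treatment-associated toxicity remains in the denominator. Without this, the amendment would create a bias of its own. For example, a transient Grade 3 ALT/AST elevation is a DLT exception in Section 4.3.1, and a patient held for it would otherwise be replaced.
3. **Section 11.1.1.1.** Align the evaluable-for-toxicity definition with item 4 for the lead-in.
4. **DLT window.** State it once; 28, 30 and 42 days all appear now.
5. **Interruption passages.** Reconcile Section 4.3.2 with the subsection on dose modification versus interruption, and say whether either applies inside the DLT window. Which clinical rule to keep is for the investigators and sponsor.

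The cost is wording, plus possibly one or two replacement patients in a lead-in expected to enrol 12, with the short delay they bring.

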4.4 Duration of Treatment

During the treatment phase, patients will receive combination therapy for 12 months or until the development of unacceptable treatment associated toxicity or confirmed progression. After the initial 12 months of therapy, patients who remain on treatment will enter the follow-up phase for the next 24 months. Patients with disease progression during the follow-up phase will have access to 12 additional months of triplet therapy. Patients who are eligible for treatment on study but who have experienced regression of all previously accessible lesions may continue on pembrolizumab and epacadostat without tavo-EP.

4.4.1 Treatment After Disease Progression

Patients with disease progression by RECIST version 1.1 who are benefiting from treatment in the opinion of the principal investigator may continue on treatment for up to 12 months from the initiation (or re-initiation) of treatment on study.

4.5 Post-Treatment Follow-up

Patients will be followed for toxicity and radiographic imaging will be performed at 3 month intervals 1) until start of a new anti-cancer treatment, (2) until 30 days after documented

disease progression, (3) until death, or (4) until 36 months from the initiation of treatment on study, whichever comes first. Each subject will be followed for overall survival until death, withdrawal of consent, or the end of the study, whichever occurs first.

4.6 Clinical and Pharmacy Considerations

4.6.1 tavo-EP

4.6.1.1 Drug Availability, Handling, and Storage

Availability

Plasmid interleukin-12 (tavo-EP) is formulated in phosphate buffered saline (PBS) for direct intratumoral injection following by *in vivo* EP. GMP-grade tavo-EP is manufactured by VGXI USA and available batches will be supplied as 2.0 mL vials at a concentration of 0.5 mg/mL and fill volume of 1.7 mL.

Storage and handling

Clinical supplies must be stored in a secure, limited-access location under the storage conditions specified on the label.

Receipt and dispensing of trial medication must be recorded by an authorized person at the trial site.

Clinical supplies may not be used for any purpose other than that stated in the protocol.

Unopened vials of tavo-EP must be stored at $-20^{\circ}\text{C} \pm 5^{\circ}\text{C}$. Once thawed, the plasmid solution will be drawn into a tuberculin syringe with a 25-gauge 5/8-inch needle. Only authorized investigators listed on the form FDA 1572 will administer the plasmid injection. Once thawed, the tavo-EP solution should be stored at 4°C and used within 8 hours as supported by in-use stability testing. Refer to the tavo Pharmacy manual for details.

Accountability

The Investigational Pharmacist will manage drug accountability records.

Drug Ordering

A 3rd party vendor CRO, will be supplying the tavo-EP to the investigational site.

Packaging and Labeling of epacadostat, pembrolizumab, and tavo-EP

Clinical supplies will be affixed with a clinical label in accordance with regulatory requirements.

Clinical Supplies Disclosure

This trial is open-label; therefore, the subject, the trial site personnel, the Sponsor and/or designee are not blinded to treatment. Drug identity (name, strength) is included in the label text; random code/disclosure envelopes or lists are not provided.

Returns and Reconciliation

The investigator is responsible for keeping accurate records of the clinical supplies received from OncoSec, Incyte or designees, the amount dispensed to and returned by the subjects and the amount remaining at the conclusion of the trial.

Upon completion or termination of the study, all unused and/or partially used investigational product will be destroyed at the site per institutional policy. It is the Investigator's responsibility to arrange for disposal of all empty containers, provided that procedures for proper disposal have been established according to applicable federal, state, local and institutional guidelines and procedures, and provided that appropriate records of disposal are kept.

4.6.1.2 Administration

Prior to plasmid injection, using sterile precautions, 1% lidocaine may be injected around the lesion to obtain local anesthesia. In addition, the patient may be given analgesics or anxiolytics as necessary prior to or during treatment. *tavo-EP:pUMVC3-hIL-12-NGVL33* (tavo-EP) will be injected intratumorally to accessible lesions without exceeding 20 mL per day. After injecting the plasmid solution into the accessible tumor, an Immunopulse® applicator containing 6 stainless steel electrodes will be inserted into the tumor such that the electrode span the plasmid injection site. The applicator will be connected to the power supply and six pulses at a field strength (E+) of 1300 V/cm and pulse width of 100 μ s at 1-second intervals will be administered to each previously injected tumor.

4.6.1.3 Treatment Parameters

Intratumoral tavo-may be administered at each odd cycle as long as the subject has at least one accessible lesion (AL) for treatment. An AL is defined as meeting the following criteria; (1) at least 0.3 cm x 0.3 cm in longest perpendicular diameters, (2) in a suitable location for application of electroporation. This includes visible or palpable sites in the oral cavity or oropharynx, palpable lymph nodes, and cutaneous lesions. Prior to initiation of a new treatment cycle of tavo-EP EP, the investigator will determine ALs for treatment during that cycle based on the most recent schedule tumor measurements. The same ALs must be treated on each day of the cycle (i.e. Days 1, 55, 8). Previously treated, previously identified lesions present at baseline that were left untreated and new lesions which appear during the course of the study that meet the definition of an AL may be treated as long as the maximum plasmid injection volume per patient per day does not exceed 20 mL. Tumors invading the carotid artery or at other sites that the investigator believes to be at high risk of life-threatening hemorrhage should not be injected.

4.6.1.4 Dose Holds

If no ALs are present at subsequent cycles, the subject may skip that cycle of tavo-EP and continue on the study calendar (**Table 3-1**). Treatment should also be held if the patient develops any sustained grade 3 or higher adverse event other than rash that is at least possibly attributed to tavo-EP in the opinion of the treating investigator. Tavo-EP may be resumed once the AE resolves to grade 1 or lower. Treatment should also be held for any intolerable rash or if holding treatment is in the best interests of the patient in the opinion of the treating investigator.

4.6.2 Epacadostat

4.6.2.1 Supply, Packaging, and Labeling

Epacadostat is available as 25, 100 and 300 mg tablets packaged in high-density polyethylene bottles.

4.6.2.2 Storage

Clinical supplies must be stored as described in the IB.

4.6.2.3 Administration

Epacadostat will be administered orally BID every 12 hours without regard to food at the dose identified in this study. If a dose is missed by more than 4 hours, then that dose should be skipped, and the next dose should be taken at the next scheduled time point. All BID doses will be taken in the morning and evening, approximately 12 hours apart.

Subjects will begin treatment with epacadostat on cycle 1, day 1 of the study and will continue administration through the end of treatment. There is no priority to the order of administration of epacadostat, pembrolizumab, and tavo-EP when administered in combination; however, the dose of epacadostat should be taken as close to the regularly scheduled 12-hour dosing interval as possible.

4.6.3 Pembrolizumab

4.6.3.1 Supply, Packaging and Labeling

See manufacturer's guidelines as described in the package insert.

4.6.3.2 Storage

See manufacturer's guidelines as described in the package insert.

4.6.3.3 Administration

See manufacturer's guidelines as described in the package insert.

5 Safety

5.1 Safety Assessments

Clinical evaluations including laboratory and clinical safety assessments will be performed at 3-week intervals for patients who are actively receiving treatment on study. For patients in the follow-up portions of the study who are not actively receiving therapy, evaluations will be performed at 12-week intervals. Safety assessments are outlined in the Study Calendar (**Table 3-1**). Safety assessments include AEs (either reported by the patient or observed by the Investigator), concomitant medication use, performance status, vital signs, physical examination, and laboratory assessments. AEs will be graded and reported using CTCAE version 4 and reported descriptively.

5.2 Safety Stopping Rules

Clinical evaluations including laboratory and clinical safety assessments will be performed at 3-week intervals for patients who are actively receiving treatment on study. For patients in the follow-up portions of the study who are not actively receiving therapy, evaluations will be performed at 12-week intervals. Safety will be assessed during the study by documentation of adverse events (AEs), clinical laboratory tests, physical examination, vital sign measurements, and Eastern Cooperative Oncology Group (ECOG) performance status.

Lead-In Period and De-Escalation

1. If, at any time, 2 or more of the first 6 safety-evaluable patients experience grade 3 or higher treatment-associated adverse events within the first 30 days of initiation of treatment, then no further patients will be enrolled at the current dose level.
2. After 6 patients have been enrolled on study, enrollment will be halted for 30 days for completion of lead-in safety analysis. If 0-1 patients experience grade 3 or higher treatment-associated adverse events within the first 30 days of initiation of treatment, then additional patients may be enrolled at the current dose level.
3. If enrollment is halted at any time during the lead-in period due to treatment-associated adverse events, the UCSF DSMB will review all available safety data with the Principal Investigator. Based on this review, study discontinuation or reduction of the epacadostat dose may be recommended. No further patients will be enrolled on study without the approval of the DSMB. If the DSMB allows additional patients to enroll, the lead-in period will be repeated at the new dose level with a maximum of 6 additional patients enrolled prior to follow-up safety analysis. At the discretion of the DSMB, patients who are currently on study may continue treatment at the reduced dose level.
4. Patients who discontinue treatment on study within 30 days of initiation of therapy for reasons other than treatment-associated toxicity will be deemed inevaluable for safety and replaced for safety analysis.

Mid-Study Interim Safety Analysis

Enrollment will also be halted for 30 days for interim safety analyses after a total of 30 safety-evaluable patients have initiated treatment on study. Patients who discontinue treatment on study within 30 days of initiation of therapy for reasons other than treatment-associated toxicity will be deemed inevaluable for safety and replaced for safety analysis. The study will be discontinued under the following circumstance:

1. On-study occurrence of 3 or more Grade 4 (life threatening) serious adverse events (SAEs) or deaths, which are deemed at least possibly related to the study agent.
2. Based on the review of data the DSMB has serious concerns about the safety of patients on the study. In addition to stopping the study, the DSMB may recommend

that the epacadostat dose for all patients be de-escalated for all current and future patients, or cessation of further patient accrual.

Safety review at participating sites

During the dose escalation safety lead-in phase of the study, weekly calls will be scheduled to review the safety data at all sites. Once the lead-in phase is completed, calls will be scheduled monthly. All sites with any active patients on study will be expected to have at least one representative on these calls. One or more representatives of the UCSF DSMC will be invited to participate as well.

6 Efficacy Assessments

MRI, contrast-enhanced CT, or PET/CT imaging of the face, neck, chest, abdomen, and pelvis are required at screening and on day 1 of each odd-numbered cycle excluding cycle 1. Both clinical and radiographic measurements may be used. All superficial, clinically apparent lesions that cannot be adequately assessed radiographically (e. g. subcutaneous lesions) must be numbered and photographed with a metric ruler visible in each photograph. For photographed lesions with borders that are not clearly visible, investigators should trace the lesions' outline, making a solid line with a felt-tipped pen. Visible lesions should never be circled with a solid line but dashed or dotted lines may be used to distinguish these markings from the borders of otherwise invisible lesions. Tumor assessments will be made using RECIST version 1.1. IL-12 plasmid dosing may be based on the most recent tumor measurements and measurements need not be repeated immediately prior to each tavo-EP treatment.

